7.4 Data Handling Conventions

7.4.1 Premature Withdrawal and Missing Data

For efficacy analyses, partial or missing dates will not be imputed. The relative study days, where determined, will be calculated for full dates only.

For rescue medication, if the time of rescue medication is missing, then all endpoints on or after the date of rescue medication will be imputed as failures.

For missing start date of AE or prior/concomitant medication, the following rules will be applied:

- If the start date is completely missing, the start date will be equal to the first dose date of study drug. However, if the stop date is not missing and is before the first dose date of study drug, then the stop date will be used instead.
- If the start day and month are missing and year is present, then the first day of the first month (January) will be used. However, if the year is the same as the year of first dose date, then the start date will be equal to the first dose date.
- If the start day is missing and year and month are present, the first day of that month will be used. However, if the year and month are the same as the year and month of first dose date, then the start date will be equal to the first dose date.

For missing stop date of AE or prior/concomitant medication, the following rules will be applied:

- If the stop date is completely missing and the medication is not ongoing, the stop date will be equal to the date of completion/withdrawal, whichever is the latest. Otherwise, if the stop date is completely missing, it will not be imputed.
- If the stop day and month are missing and year is present, then the last day of the last month (December) will be used. However, if the year is the same as the year of date of completion/withdrawal, then the stop date will be equal to the date of completion/withdrawal.
- If the stop day is missing and year and month are present, the last day of that month will be used. However, if the year and month are the same as the year and month of date of completion/withdrawal, then the stop date will be equal to the date of completion/withdrawal.

These imputed dates will be used to determine whether the AEs or medications are on-treatment.

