7.5.5 Prior and Concomitant Therapies

Non-study medications will be coded into Anatomical Therapeutic Chemical (ATC) classification codes and preferred drug names using the World Health Organization (WHO) Drug <DDE (Enhanced) B3 Format, March 2020 or later>. For each subject, multiple records of the same medication will be counted only once within each ATC Level 2 and/or PT term.

The following non-study medications will be tabulated:

Prior medications are defined as those taken before study drug, i.e., imputed start or stop date < study drug start date. These include the following two subtypes:

- Prior medications, defined as those taken before informed consent, i.e., those with an imputed start or stop date < informed consent date.
- Current medications, defined as those taken on or after informed consent and before study drug, i.e., those with (1) informed consent date ≤ imputed start or imputed stop date ≤ study drug start date – 1, or (2) imputed start date ≤ informed consent date ≤ study drug start date – 1 ≤ imputed stop date.
- Concomitant medications, defined as those taken on or after study drug, i.e., study drug start date ≤ imputed start or stop date.
- Prior prophylactic medications
- Current prophylactic medications
- Concomitant prophylactic medications

All prior, current and concomitant medications will be included in a listing. Additionally, non-drug therapies will be provided in a listing only.

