7.7.2 Adverse Events

All Adverse Events (AEs) will be coded using the MedDRA version 23.0 or later. AEs toxicities will be graded according to National Cancer Institute Common Terminology Criteria for Adverse Events (NCI CTCAE), Version 5.0.

All AEs will be summarized for the following categories: AEs with onset prior to randomization, AEs with onset on or after randomization but prior to study treatment, and treatment emergent adverse events (TEAEs) with onset on or after study treatment respectively.

An overall summary of AEs, which includes the number and percentage of subjects reporting any AEs, AEs with onset prior to randomization, AEs with onset on or after randomization but prior to study treatment, serious AEs with onset prior to randomization, serious AEs with onset on or after randomization but prior to study treatment, TEAEs, drug-related TEAEs, TEAEs with CTCAE grade ≥ 3 , serious TEAEs, drug-related serious TEAEs, non-serious TEAEs, and TEAEs

leading to death will be presented. The number and percentage of subjects by SOC and PT will also be reported.

In the event of multiple occurrences of the same AEs being reported by the same subject, the maximum NCI-CTC Grade (Grade 5 > Grade 4 > Grade 3 > Grade 2 > Grade 1 > missing > not applicable) will be presented in the summary tables. A subject will be counted once at the highest grade for which the event occurred at the SOC level and the highest grade for each unique PT within that SOC level. Therefore, subjects may only contribute once to each PT and once to each SOC level. If CTCAE grade is missing for one event and the subject had no Grade ≥ 1 in the same category, “missing” row/column should be added in the summary tables with maximum CTCAE grade. The following summary tables will present the number and percentage of subjects by SOC, PT and maximum CTCAE grade.

- ◊ TEAEs
- ◊ Drug-related TEAEs

The following tables summarizing the number and percentage of subjects by SOC and PT will present only those TEAEs that occurred in at least 5% in at least one treatment group.

- ◊ TEAEs
- ◊ Drug-related TEAEs

All AEs will be included in listings. TEAEs are labelled in the listings. Listings will be provided for Serious Adverse Events (SAEs), AEs related to study drug, and grade >2 AEs separately. SAEs occurring in subjects enrolled but not treated will also be provided. AE leading to deaths will be listed for all enrolled subjects without regard to onset.

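### SAP 7.4.1 checks a known stop date only when the start date is completely missing, so some adverse events that ended before dosing would be counted as treatment-emergent

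*SAP*

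**What the plan says.** SAP 7.4.1 has three rules for an incomplete start date of an AE or a prior or concomitant medication.

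- **Start completely missing.** The start becomes the first dose date, with an exception: "if the stop date is not missing and is before the first dose date of study drug, then the stop date will be used instead".
- **Only the year known.** The default is 1 January of that year. The exception is that "if the year is the same as the year of first dose date, then the start date will be equal to the first dose date".
- **Year and month known.** The default is the first of that month. Here too an exception moves the start to the first dose date: "if the year and month are the same as the year and month of first dose date, then the start date will be equal".

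The section then gives the purpose of the results: "These imputed dates will be used to determine whether the AEs or medications are on-treatment".

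Two later sections use these dates. SAP 7.7.2 separates "AEs with onset on or after randomization but prior to study treatment" from "treatment emergent adverse events (TEAEs) with onset on or after study treatment", so the split rests on onset alone. SAP 7.5.5 defines prior medications by "imputed start or stop date < study drug start date". It also has a category "Concomitant medications, defined as those taken on or after study drug", met when the imputed start or the stop falls on or after the study drug start date.

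**The concern.** The second and third rules never refer to the stop date. If the known part of the start matches the dosing year or month, the record moves to the dosing day even when its stop date shows that it was over by then. It then has a start later than its stop. Because treatment emergence depends only on onset, nothing later in the SAP corrects it.

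The result also runs against the information available. A record with no start date at all is classified correctly, while one with a year, or a year and month, is not. The first rule shows that the SAP recognises the problem but guards against it in only one of three cases.

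The design allows such records to arise. Non-serious AEs are collected from the Baseline visit (Protocol 8.2.1) and serious AEs from consent (Protocol 8.1.2). The subject may hold the study drug for up to 45 days before dosing (Protocol 4.3.2). For medications, Protocol 5.4 requires several products, including traditional Chinese medicines and St. John's Wort, to be stopped 14 days before randomization. A product that was washed out correctly, with only the current year recorded as its start, could appear in the concomitant table.

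At stake are the accuracy of the treatment-emergent AE (TEAE) and concomitant-medication counts, and the consistency of the dates behind them.

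**Working it through.** This is a date rule, so the plan has no figure to reproduce. The check runs example records through the three rules as written, then applies the definitions in SAP 7.7.2 and 7.5.5. All dates are illustrative; the first dose is 20-Sep-2021.

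| Recorded start | Known stop | Start under SAP 7.4.1 | TEAE? | Start with the fix | TEAE? |
|---|---|---|---|---|---|
| completely missing | 08-Sep-2021 | 08-Sep-2021 | no | 08-Sep-2021 | no |
| 2021 | 08-Sep-2021 | 20-Sep-2021 | **yes** | 08-Sep-2021 | no |
| Sep-2021 | 08-Sep-2021 | 20-Sep-2021 | **yes** | 08-Sep-2021 | no |
| 2021 | 03-Mar-2021 | 20-Sep-2021 | **yes** | 03-Mar-2021 | no |
| Sep-2021 | 25-Sep-2021 | 20-Sep-2021 | yes | 20-Sep-2021 | yes |
| Aug-2021 | 08-Sep-2021 | 01-Aug-2021 | no | 01-Aug-2021 | no |

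In rows 2 and 3 the imputed start is 20 − 8 = 12 days after the stop. Row 5 is ordinary conservative imputation and does not change. Row 6 shows that the first-of-month default already works.

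**Medications.** Take the dates in rows 2 to 4 for a medication. The stop is before dosing, so the prior definition is met. The imputed start is on the dosing day, so the concomitant definition is met too. The record is counted in both categories. With the fix it is prior only.

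**How often the rule fails, given a record at risk.** All date combinations were enumerated with equal weight: randomization on any day of 2022, dosing 1 to 45 days later, and an AE lasting 1 to 4 days that starts on or after randomization and ends before dosing. Only the 45-day limit comes from the documents; the rest is assumed.

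| Missing part of the start date | Falsely treatment-emergent, as written | With the fix |
|---|---|---|
| day only | about 47% | 0% |
| day and month | about 95% | 0% |

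The first share is the chance that the AE started in the dosing month. The second is the chance that it started in the dosing year. Both are shares of wholly pre-dose AEs that have a partial start date and a known stop date. They are not shares of all AEs, and they give no count.

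**The case against.** The case for leaving the text alone is that few records can be affected. Three things must coincide: a partial start date, a known stop date before dosing, and a known part that matches the dosing month or year. Subjects keep a take-home log of AEs and medications (Protocol 5.4.1 and 6.1), and the whole study lasts about 11 weeks (Protocol 4.1). A year-only start for an AE with a known stop date would be unusual in that setting. This stands, and it limits the size of the point. It does not make the rule correct.

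The consequences are limited too. The rule is identical in both arms of a double-blind trial. Relatedness is decided by the investigator (Protocol 9.4.5), so moving a date does not make an event drug-related. The TEAE tables by preferred term with a 5% cut-off need 0.05 × 600 = 30 subjects in an arm of about 600 treated, so a few moved records would not by themselves bring a term to that level. All AEs are listed with TEAEs labelled (SAP 7.7.2), so affected records could be found. These points also stand.

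A reader might go further and infer three things that the documents do not support:

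- **That the safety comparison is materially distorted.** Neither document gives a rate of partial dates, so no number of false TEAEs can be derived.
- **That affected medications are lost from the prior category.** Under SAP 7.5.5 they stay prior and are additionally counted as concomitant.
- **That imputing to the dosing date is wrong in itself.** When the stop date is missing, or falls on or after dosing, the timing is uncertain and the rule is a reasonable conservative choice. The fault is confined to records whose stop date settles the question.

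**Conclusion.** The point holds in this limited form. As written, the year-only and year-and-month rules in SAP 7.4.1 turn an AE known to have ended before dosing into a TEAE with a start after its stop. They also add a pre-dose medication to the concomitant count. No other section of the protocol or SAP overrides this.

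The conclusion assumes that the rules are programmed as written and that the stop date is known. The number of affected records is not stated and is probably small, and no direction between arms is evident. Efficacy is untouched, because SAP 7.4.1 excludes partial dates from imputation in efficacy analyses. This is a correction to the safety derivations and does not threaten the trial's conclusions. It is still worth making: without it, the programmer must either produce impossible date pairs or depart from the SAP without documentation.

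**What to change.** In SAP 7.4.1, change only the 'However' clauses of the second and third start-date bullets. Where either clause would assign the first dose date, add the first bullet's condition: if the stop date is not missing and is before the first dose date, use the stop date instead. Then state that an AE with a known stop date before first dose is not treatment-emergent, and that a medication with such a stop date is not concomitant.

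Leave the 1 January and first-of-month defaults unchanged. A single formula for all three bullets, such as the earlier of first dose and stop date, would create a new error. With start Aug-2021, stop 25-Sep-2021 and dose 20-Sep-2021, it would give 20-Sep-2021, a false TEAE that contradicts the known month; the present rule correctly gives 01-Aug-2021.

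The cost is a sentence or two in the SAP and one extra condition in the imputation program. No additional data are needed.

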7.4.2 Derived and Transformed Data

Calculation of Study Day

Study day describes the day of assessment/event date relative to the randomization date. It will be defined as:

- Date of assessment/event – randomization date + 1, if date of assessment/event is at or after randomization
- Date of assessment/event – randomization date, if date of assessment/event is prior to randomization

7.5 Study Subjects

7.5.1 Disposition of Subjects

A summary of subject disposition will be tabulated for all enrolled subjects by treatment group and overall. The disposition table will support the creation of a consort diagram. The categories in the table will include:

- Number of subjects screened
- Number of screen failed subjects and reason for screen failure
- Number of subjects randomized
- Number of subjects not treated, and the reasons for not being treated
- Number of subjects treated
- Completed Study
- Discontinued, and reasons for discontinuation
- Number of subjects in each analysis population

A by-subject listing of subject disposition information, including the reason for discontinuation, if applicable, will be presented.

7.5.2 Protocol Deviations

The major protocol deviations will be tabulated by category based on randomized subjects. All major protocol deviations will be listed by subject based on medical review.

7.5.3 Demographic and Baseline Characteristics

Demographic and baseline characteristics will be summarized by as-randomized treatment group and overall for the mITT population including: age, gender, childbearing potential for females, country, weight, height, body mass index (BMI), history of allergies (yes vs. no). A similar table will be made for the treated population by as-treated treatment group and overall to support safety.

A separate set of tabulation of demographic information will be made for subjects enrolled but not randomized (overall only) and subjects randomized but not treated (by as-randomized treatment group and overall).

The migraine history will be summarized by as-randomized treatment group and overall for the mITT population including but not limited to: age at migraine onset, experience migraines for at least one year prior to screening (yes vs. no), migraine history in years, duration of migraine attacks, number of moderate or severe migraines per month within last 3 months, use of prophylactic migraine medications (yes vs. no), primary migraine type. A similar table will be made for the treated population by as-treated treatment group and overall to support safety.

Demographic and baseline characteristics, and migraine history will be listed for all randomized subjects.

7.5.4 Medical History

Medical history will be coded using the Medical Dictionary for Regulatory Activities (MedDRA) version 23.0 or later.

Based on the mITT population with as-randomized treatment group, the medical history data will be summarized with frequencies and percentages of subjects with at least one medical history, and subject frequencies and percentages on the System Organ Class (SOC) and Preferred Term (PT) levels. The table will be sorted by overall descending frequency of SOC and then, within a SOC, by overall descending frequency of PT. A similar table will be made for the treated population by as-treated treatment group and overall to support safety.

Medical history will be listed by subject.

7.5.5 Prior and Concomitant Therapies

Non-study medications will be coded into Anatomical Therapeutic Chemical (ATC) classification codes and preferred drug names using the World Health Organization (WHO) Drug <DDE (Enhanced) B3 Format, March 2020 or later>. For each subject, multiple records of the same medication will be counted only once within each ATC Level 2 and/or PT term.

The following non-study medications will be tabulated:

Prior medications are defined as those taken before study drug, i.e., imputed start or stop date < study drug start date. These include the following two subtypes:

- Prior medications, defined as those taken before informed consent, i.e., those with an imputed start or stop date < informed consent date.
- Current medications, defined as those taken on or after informed consent and before study drug, i.e., those with (1) informed consent date ≤ imputed start or imputed stop date ≤ study drug start date – 1, or (2) imputed start date ≤ informed consent date ≤ study drug start date – 1 ≤ imputed stop date.
- Concomitant medications, defined as those taken on or after study drug, i.e., study drug start date ≤ imputed start or stop date.
- Prior prophylactic medications
- Current prophylactic medications
- Concomitant prophylactic medications

All prior, current and concomitant medications will be included in a listing. Additionally, non-drug therapies will be provided in a listing only.

7.5.6 Compliance

Considering the study drug will be administrated once for each subject, the treatment compliance will be not calculated and summarized.

The eDiary compliance at 2, 4, 6, 8, 24, and 48 hours post-dose by counting the number of subjects with missing data will be summarized using the mITT population.

7.6 Efficacy Analyses

Unless otherwise noted, all efficacy analyses will be conducted using the mITT population as outlined below. Efficacy tabulations will present results by as-randomized treatment group only (excluding overall), unless specified otherwise. All efficacy data will be included in listings by subject, treatment group, and time point (as applicable).

7.6.1 Primary Efficacy Analyses

The co-primary efficacy endpoints are pain freedom at 2 hours post-dose and freedom from MBS at 2 hours post-dose.

7.6.1.1 Pain Freedom at 2 Hours Post-Dose

Pain freedom is assessed using the number of mITT subjects that report pain levels of “none” at 2 hours post-dose on a 4-point Likert scale (0=none, 1=mild, 2=moderate, 3=severe). The information from the 4-point scale is directly summarized as follows:

A table showing descriptive statistics for the observed data, which includes the number and percentage of subjects reporting each of the 4 pain levels at baseline and each post-dose timepoint, and the percentage of subjects with missing data, for each treatment group. The table will include exact (Clopper-Pearson) 95% CIs for each percentage.

The difference in percentage of pain freedom at 2 hours post dose between treatment groups is evaluated by computing the common risk difference, using Cochran-Mantel-Haenszel (CMH) weights (sample size weights), stratified by the use of prophylactic migraine medication (yes or no) and country (China or Korea). The risk difference is tested at a two-sided alpha level of 0.05. Missing data at 2 hours post-dose will be imputed as failures (i.e., non-Completers = Failure; NC=F). Subjects that use rescue medication prior to reporting pain freedom at 2 hours will be classified as failures (i.e., Rescue Medication = Failure; RM=F). If a stratum (prophylactic medication use: yes or no) has sparse data (less than 5 subjects), then the strata will be pooled.

A forest plot of the risk differences within each stratum, and common risk difference (similar to the risk difference plot produced by SAS Proc Freq) will be provided.

Sensitivity analyses will be conducted as follows:

1. The primary analysis is repeated, using the mITT population, with missing data at 2 hours post-dose imputed using Last Observation Carried Forward (LOCF). Baseline Observation Carried Forward (BOCF) is permitted.
2. The primary analysis is repeated using only data from complete cases (data present at baseline and 2 hours).

A sample SAS code for exact (Clopper-Pearson) 95% CIs is the following:

```
proc freq data=pain;
  by treatment pain_level;
  table response / binomial (level="1" CL=(EXACT));
  weight count;
run;
```

A sample SAS code for common risk difference from Mantel Haenszel method is the following:

```
proc freq data=pain_2h;
  table prophylactic_migraine_medication*country*treatment*response /riskdiff (common
  CL=(WALD)) CMH ;
  weight count;
run;
```

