previously published migraine studies [19]. rimegepant at 75 mg showed statistically significant broad efficacy across all four traditional endpoints at 2 hours (pain, nausea, photophobia and phonophobia) which was durable and persisted through 24 hr. At 2 hours following a single oral dose of 75 mg, subjects who previously were experiencing moderate-to-severe migraine pain had no-pain (31.4% p = 0.0018) or mild-to-no-pain (72.1%) as compared to placebo (15.3% and 51.2%, respectively). For the 75 mg dose at 2 hours, subjects also showed significant freedom from nausea (67.4%, p = 0.0074) freedom from phonophobia (52.3%, p = 0.0001) and freedom from photophobia (41.9%, p = 0.0023) vs. placebo (51.2%, 28.1% and 24.1%, respectively). The lasting nature of these beneficial anti-migraine effects were evidenced by a comparatively similar efficacy profile in the 2-24 hour measures, where rimegepant at 75 mg produced significant 2-24 hour sustained pain freedom (27.9%, p < 0.0001) and 2-24 hour sustained pain relief (69.8%, p < 0.0001) vs. placebo (7.4% and 42.4%, respectively).

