
From Table 2, it can be seen that the placebo response rates for MBS freedom at two hours post-dose range from 25.2% to 27.7%. The therapeutic gains range from 8.3% to 12.4%. The p-values ranged from < 0.0001 to 0.0016.

| Table 2: Response Rates and Therapeutic Gains for MBS Freedom at 2 Hours Post-Dose | | | |
|--|-----------------|-----------------|-----------------|
| | BHV3000-301 | BHV3000-302 | BHV3000-303 |
| Rimegepant Group | 36.6% (199/543) | 37.6% (202/537) | 35.1% (235/669) |
| Placebo Group | 27.7% (150/541) | 25.2% (135/535) | 26.8% (183/682) |
| Therapeutic Gain | 8.9% | 12.4% | 8.3% |
| p-value | 0.0016 | <0.0001 | 0.0009 |

Outline of Power Calculations

Based on the 3 studies described above, a range of plausible response rates and therapeutic gains were chosen as the basis for a series of power calculations. These values are shown in Table 3. It can be seen from the table that the ranges of placebo rates and therapeutic gains selected for the power analyses roughly span the ranges observed in the 3 previous studies.

| Table 3: Response Rates and Therapeutic Gains Selected for Power Analyses | | | |
|---|-------------------------|----------------------------|--|
| | Pain Freedom | MBS Freedom | |
| Placebo Rates | 11%, 12%, 13%, 14% | 25%, 26%, 27%, 28% | |
| Therapeutic Gains | 5%, 6%, 7%, 8%, 9%, 10% | 8%, 9%, 10%, 11%, 12%, 13% | |

To conduct the power analyses all values of the placebo rates were paired with all values of the therapeutic gains. For example, for pain freedom, there are 4 values for the placebo rates and 6 values for the therapeutic gains, so power analyses were conducted for $4 \times 6 = 24$ pairs of values. Similarly, for MBS freedom, power analyses were conducted at $4 \times 6 = 24$ pairs of values.

The power calculations were conducted using the Pearson Chi-Square test, a two-sided alpha of 0.05, and all of the pairs of placebo rates and therapeutic gains described above. The target sample size for BHV3000-310 is 600 evaluable subjects per treatment arm. Hence, all of the calculations were conducted at that sample size. The calculations were executed using SAS PROC POWER, with the TWOSAMPLE FREQ and TEST=pchi options.

Power Calculations for Pain Freedom

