13. The proportion of subjects able to function normally from 2 to 48 hours post-dose, will be assessed using the number of subjects that self-report as “normal” on the FDS through the time period of interest.
14. Time to rescue medication use up to 24 hours pose-dose
15. Time to first report of pain freedom up to 8 hours pose-dose
16. Time to first report of freedom from MBS up to 8 hours pose-dose
17. Time to first report of pain relief up to 8 hours pose-dose
18. Time to first report of absence of nausea up to 8 hours pose-dose
19. Time to first report of absence of photophobia up to 8 hours pose-dose
20. Time to first report of absence of phonophobia up to 8 hours pose-dose
21. Time to first report of return to normal functioning up to 8 hours post dose

5 Sample Size

If roughly 85% of the 715 subjects randomized to each treatment arm have a migraine in the allotted time period, there will be approximately 600 treated subjects per group.

Based on data from studies BHV3000-301 and BHV3000-302, 600 treated subjects provides 95% power to detect a difference between rimegepant and placebo on the subject’s self-reported most bothersome symptom. Also, 600 subjects provides 95% power to detect a difference in freedom from pain at 2 hours. Having at 95% power on each co-primary endpoint provides roughly 90% power to detect a difference on both endpoints jointly.

6 Analysis Sets

The following analysis sets will be evaluated and used for presentation and analysis of the data:

- Enrolled subjects: Subjects who sign an informed consent form and are assigned a subject identification number.
- Randomized subjects: Enrolled subjects who receive a randomization treatment assignment from the IWRS (rimegepant or placebo).
- Treated subjects: Enrolled subjects who take study therapy (rimegepant or placebo).
- Modified Intent to Treat (mITT) subjects: randomized subjects that take study therapy, have a migraine of moderate or severe intensity at the time of treatment, and provide at least one post-treatment efficacy data point.

No separate per protocol analysis set is defined for this study. There will not be any per protocol analysis conducted for this study.

7 Statistical Methods

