7.2 Adjusting of Covariates

The randomization is stratified by the use of prophylactic migraine medication (yes or no) and country (China and Korea). Hence, most analyses are stratified by the use of prophylactic medication and country.

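### The co-primary analyses are valid but leave pre-dose pain intensity and the nominated most bothersome symptom unused, so a small and uncertain gain in precision is passed over

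*SAP*

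**What the plan says.** SAP 7.6.1.1 (pain freedom) and 7.6.1.2 (MBS freedom) use a common risk difference with Cochran-Mantel-Haenszel (CMH) weights, "stratified by the use of prophylactic migraine medication (yes or no) and country (China or Korea". Protocol 9.4.1 names the same two factors. SAP 7.2 gives the reason, which is that these are the randomization factors: "Hence, most analyses are stratified by the use of prophylactic medication and country". For each endpoint, "The risk difference is tested at a two-sided alpha level of 0.05".

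Two further values are entered in the eDiary before dosing by design (Protocol 4.3.2.1 and 6.3.2): headache intensity and the current MBS. Membership of the mITT set (SAP section 6) requires that a subject "have a migraine of moderate or severe intensity at the time of treatment", so pre-dose pain has exactly two levels there. Both values appear in descriptive tables in 7.6.1.1 and 7.6.1.2. Neither is a stratification factor or covariate, and neither is a subgroup factor in 7.9.1. The sensitivity analyses in 7.6.1.1 and 7.6.1.2 vary only the handling of missing data.

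**The concern.** A subject who doses at severe pain has further to go to reach no pain than one who doses at moderate pain, so pre-dose intensity is a natural predictor of pain freedom. The nominated symptom may also predict MBS freedom. In the Phase 2b trial the 2-hour freedom rates on 75 mg for nausea, phonophobia and photophobia were 67.4%, 52.3% and 41.9% "vs. placebo (51.2%, 28.1% and 24.1%, respectively" (Protocol 1.3.2). Adjusting for prognostic baseline values narrows the confidence interval and removes chance imbalance in severity or symptom mix.

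This could matter because the trial must win on both endpoints, and the margin shrinks quickly if the pain effect is modest. Appendix IV Table 4 gives 89.2 to 93.2% power for a 7-point gain, 79.1 to 85.1% for 6 points and 64.6 to 71.8% for 5 points. Study BHV3000-301 observed 4.9 points.

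**Working it through.** **Inputs from the documents.** "The target sample size for BHV3000-310 is 600 evaluable subjects per treatment arm"; "The power calculations were conducted using the Pearson Chi-Square test, a two-sided alpha of 0.05". Reference cases are the lowest-power rows that still exceed 95%: pain freedom 14% v 22% (stated 95.1%) and MBS freedom 28% v 38% (stated 95.8%).

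**Inputs not in the documents, therefore assumed.** Severe share 20 to 50%; moderate-to-severe response ratio 1 to 3; nausea as MBS in 20 to 50%; nausea response 1.25 to 1.5 times that of the other symptoms, or the Phase 2b contrast as an upper proxy.

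**1. Reproduce the plan's power.** Power = Φ{[Δ√n − 1.96√(2p̄(1−p̄))] / √V}, with V = p0(1−p0) + p1(1−p1).
- Pain: (0.08×24.495 − 1.96×√(2×0.18×0.82)) / √0.2920 = (1.9596 − 1.0649)/0.5404 = 1.656, giving 95.1%.
- MBS: (0.10×24.495 − 1.96×√(2×0.33×0.67)) / √0.4372 = (2.4495 − 1.3033)/0.6612 = 1.733, giving 95.8%.

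All 48 entries of Tables 4 and 5 reproduce within 0.05 points.

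**2. Variance removed by a prognostic factor.** With level shares w_k, V_adj = Σ w_k[p0k(1−p0k) + p1k(1−p1k)]. The reduction is 1 − V_adj/V, worth 600(V/V_adj − 1) extra subjects per arm.
- Pain, upper end (50% severe, ratio 3 in both arms): placebo 21%/7%, drug 33%/11%. V_adj = 0.1155 + 0.1595 = 0.2750. Reduction 1 − 0.2750/0.2920 = 5.8%, or 37 per arm.
- Pain, moderate case (30% severe, ratio 2 on placebo, equal risk difference): placebo 16.5%/8.2%. Reduction 2×0.7×0.3×0.0824²/0.2920 = 1.0%, or 6 per arm.
- MBS, lower end (20% nausea, ratio 1.25 on placebo, equal risk difference): placebo 33.3% v 26.7%. Reduction 2×0.2×0.8×0.0667²/0.4372 = 0.3%, or 2 per arm.
- MBS, Phase 2b placebo contrast scaled to 28% and 38% (nausea/phonophobia/photophobia 30/15/55): placebo 43.7%, 24.0%, 20.5%. Between-symptom variance is 0.01066 on placebo and 0.01964 on drug. Reduction 0.0303/0.4372 = 6.9%, or 45 per arm.

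**3. Effect on power.** These figures use the unpooled variance, so the starting values differ by about 0.1 to 0.2 points from Appendix IV.

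| Case | Now | With adjustment |
|---|---|---|
| Pain 14% v 22% | 95.2% | 95.2 to 96.2% |
| MBS 28% v 38%, nausea ratio 1.25 to 1.5 | 95.9% | 96.0 to 96.3% |
| MBS 28% v 38%, Phase 2b contrast | 95.9% | 96.6 to 97.0% |
| Pain 14% v 19% | 64.7% | at most 67.0% |
| MBS 28% v 36% | 84.6% | at most 87.0% |

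**4. Is the Phase 2b contrast a fair proxy?** Those rates are by symptom, not by nominated MBS. Combine them with a nausea share of 15 to 30%. If everyone else nominates photophobia, 15% nausea implies 0.15×51.2 + 0.85×24.1 = 28.2% on placebo and 0.15×67.4 + 0.85×41.9 = 45.7% on drug. If everyone else nominates phonophobia, 30% nausea implies 35.0% and 56.8%. Appendix IV Table 2 shows 25.2 to 27.7% and 35.1 to 37.6%. The drug figure misses by at least 45.7 − 37.6 = 8.1 points, so the 4.0 to 6.9% reduction from this proxy is an upper bound and not an estimate.

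**5. How the adjustment is made.** Simulated at the reference rates (assumed 20% Korea, 10% prophylactic use, 30% severe, symptom mix 25/20/55):
- Extra CMH strata, 4 becoming 8 (pain) or 12 (MBS): variance ratio new/old 1.003, 1.000, 0.994, 0.984 for pain at response ratio 1, 1.5, 2, 3. For MBS it is 1.008, 1.002, 0.991 at nausea ratio 1, 1.25, 1.5, and 0.959 under the Phase 2b contrast. Power changes by −0.1 to +0.7 points.
- Main-effects linear model with robust variance, against adjustment for the two planned factors: ratio 1.001 for both endpoints when the factor is not prognostic; 0.996, 0.985, 0.971 for pain at ratio 1.5, 2, 3. The best power gain was about 0.9 points. A repeat with a standardized logistic model also lost almost nothing when the factor was not prognostic.

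**The case against.** The case for leaving the plan alone is substantial. The analysis uses exactly its randomization factors, is valid, and meets its stated power under an unstratified test that counts on no covariate gain. With about 600 per arm, chance imbalance does not invalidate the test. The pain half has no documentary input at all, and the MBS half leans on a proxy that conflicts with the Phase 3 totals. All of this stands, and it limits the point to an optional improvement.

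The practical objections also stand against simply adding strata. The SAP's pooling rule for sparse data is written only for prophylactic use. Subjects who dose before naming an MBS, or never name one, stay in the analysis as failures (SAP 7.6.1.2) and have no stratum level. SAP 7.1 sets the efficacy baseline at migraine onset, whereas the mITT definition uses pain at treatment, so the rating has to be named. Many later endpoints, including relapse among subjects pain-free at 2 hours, borrow the method of 7.6.1.1 and would meet sparse cells.

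These objections do not defeat a main-effects model limited to the two co-primary endpoints, because it loses almost nothing if the factors turn out not to be prognostic. Both values are recorded after randomization but, by design, before dosing and under blind, so they can serve as baseline covariates.

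**Conclusion.** The point holds as a minor efficiency improvement. Two pre-dose values that the trial already collects are left out of the co-primary analyses. On the assumed inputs the variance reduction is about 0 to 6% for pain freedom and 0.3 to 7% for MBS freedom, with the top of the MBS range only under the Phase 2b proxy. That is 0 to 1 power point at the design rates and at most about 2 points at smaller effects. No single figure can be given, because the documents report neither the severe share, nor response by pre-dose pain, nor the MBS mix.

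A reader might infer more than this, and the documents do not support it:
- That the co-primary analysis is wrong or the trial underpowered for want of these covariates. It is neither.
- That the gain is certain. Nothing in the documents shows how strongly either value predicts the endpoint, and extra CMH strata for a weak factor give no gain or a variance loss of up to 0.8%.
- That the change is free. No new data are needed, but Protocol 9.4.1 fixes the factors and SAP 7.10 declares no departure from the protocol.

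**What to change.** Before unblinding, and for the two co-primary endpoints only:
- Pre-specify a standardized (marginal) risk difference, with robust variance, from a main-effects model with treatment, prophylactic use, country and pain intensity at the time of treatment (not at onset).
- For MBS freedom, add the nominated symptom with a fourth category for subjects who reported none or dosed first. They remain failures. Since everyone in that category fails by rule, a logistic coefficient for it would not converge, so specify a linear working model or set the predicted risk there to zero.
- Keep the four-stratum CMH risk difference as supportive, and do not add CMH strata.
- Align Protocol 9.4.1 and record the change in SAP 7.10.

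If a change of primary model is unwelcome, add the adjusted analysis as a pre-specified sensitivity analysis for each co-primary endpoint and leave the primary as it is.

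The cost is wording: a SAP revision and, if the primary analysis changes, a protocol amendment under Protocol section 11. The other downside is a primary model that is less simple than a stratified risk difference.
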